- **Data directly provided by the participant:** While using the *Messy Memories* application, participants will use affect rating sliders to directly input information related to their mood over the past several days, their level of distress before and after processing a difficult memory, and answers to questions about revisiting their difficult memory. Direct recordings of the participant's "messy memory" (audio recorded) will only be available on the participant's smartphone while using the app. These recordings (audio) will not be collected as data.
- **Data indirectly provided by the participant:** The *Messy Memories* application will also collect data on how long and how frequently participants use the application. Specifically, each response to a prompt within the application will be recorded with a timestamp (date and time) to indicate when the participant provided a particular response.
- **Protected Health Information (PHI):** The *Messy Memories* application does not collect or store PHI. Participants will be instructed not to record any identifiable information while using the app.

Measures:

Feasibility: To assess feasibility of the intervention, we will determine: 1) the number of participants that are needed to screen and consent; 2) the proportion of eligible participants who accept the offer to participate; 3) the proportion of consenting participants who download the application and initiate the intervention (i.e., log into the app at least once after the baseline visit); 4) the proportion of consenting participants who access the Memory Processing module at least once; 5) the total number of times that the Memory Processing module is accessed; 6) the total number of times that each additional modules (i.e., Introduction, Feedback) is accessed. We will also describe how participants generally engage with the app (e.g., frequency and duration of engagement with each feature). In addition, we will assess the relative efficacy of each of our recruitment strategies.

Acceptability: To assess acceptability of the intervention, participants will be asked to complete an exit survey via telephone interview or self-administered online. The survey will include questions regarding perceptions and feelings about the intervention. Participants will also be asked to provide qualitative feedback on the intervention (e.g., likes, dislikes, suggestions for improvement).

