Proctor's Implementation Measures: Three validated measures (Acceptability of Intervention Measure [AIM], Feasibility of Intervention Measure [FIM], and Intervention Appropriateness Measure [IAM]) will be used to assess the acceptability, feasibility, and appropriateness of the *Messy Memories* intervention, respectively.⁵⁶ Each measure consists of four items answered on a 5-point scale (1 = *strongly disagree*, 5 = *strongly agree*). Average responses of ≥ 4 on the AIM, FIM, and IAM are indicative of adequate acceptability, feasibility, and appropriateness, respectively.^{56,57}

System Usability Scale (SUS): The SUS is a reliable tool for evaluating the usability of various products and services, including hardware, software, mobile devices, websites, and applications.^{58,59} It consists of ten items answered on a 5-point scale (1 = *strongly disagree*, 5 = *strongly agree*). We will use a score ≥ 68 to indicate adequate usability, in accordance with prior studies.⁶⁰

PTSD symptoms: PTSD symptoms triggered by the prior critical illness and ICU hospitalization will be assessed using the PTSD Checklist for the Diagnostic and Statistical Manual of Mental Disorders, 5th Edition (PCL-5).⁶¹ The PCL-5 is an extensively validated self-report measure developed by the National Center for PTSD that corresponds to DSM-5 criteria for PTSD. Patients are provided a list of 20 PTSD symptoms and asked to rate how much they have been bothered by each symptom due to their prior critical illness and ICU hospitalization on a scale of 0 = *not at all* to 4 = *extremely*. We will classify participants with PCL-5 scores ≥ 34 as having elevated PTSD symptoms, which has been validated as a screening cutoff and used in prior studies of civilian populations.⁶²⁻⁶⁴

Other psychological symptoms: In addition to PTSD symptoms, we will also assess for symptoms of depression, anxiety, and anxiety sensitivity. Depression will be assessed using the 8-item Patient Health Questionnaire (PHQ-8),⁶⁵ with scores ≥ 10 positive for depression.^{66,67} Anxiety will be assessed using the 7-item Generalized Anxiety Disorder (GAD-7) scale,⁶⁸ with scores ≥ 10 positive for anxiety.⁶⁹ Anxiety sensitivity will be assessed using the 16-item Anxiety Sensitivity Index (ASI),⁷⁰ with scores ≥ 17 indicating high anxiety sensitivity.⁷¹

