Descriptive statistics: Categorical data will be presented as percentages and continuous data will be presented as means with standard deviations for normally distributed measures and as medians with interquartile ranges for measures that are not normally distributed. Checks of assumptions (e.g., normality) underlying statistical procedures will be performed and corrective procedures will be applied (e.g., log transformations, nonparametric tests).

Outcomes: The primary outcomes are feasibility and acceptability of the *Messy Memories* intervention and research procedures. Feasibility will be based on participant recruitment, retention, and completion rates of $\geq 70\%$. Acceptability will be based on participant satisfaction ratings of $\geq 70\%$ and qualitative analysis of exit survey responses. The *exploratory outcome* is the ability of the *Messy Memories* intervention to engage the proposed mechanistic target, which will be based on pre-/post-intervention change in patient-reported PTSD symptoms specifically triggered by the prior critical illness and ICU hospitalization.

Aim 1: Assess the feasibility of recruiting and engaging critical illness survivors in a mobile application-based exposure therapy intervention (*Messy Memories*). **Hypothesis:** The intervention will be feasible based on recruitment, retention, and completion rates of $\geq 70\%$.

Aim 2: Assess the acceptability of recruiting and engaging critical illness survivors in a mobile application-based exposure therapy intervention (*Messy Memories*). **Hypothesis:** The intervention will be acceptable based on participant satisfaction ratings of $\geq 70\%$ and qualitative analysis of exit survey responses.

Statistical approach for Aims 1 & 2: We will calculate means and standard deviations (or medians and interquartile ranges if variables are non-normal) as well as frequencies and proportions to assess feasibility and acceptability outcomes. T-tests or chi-square tests will be used to compare the demographic and clinical characteristics of 1) eligible patients who did vs. did not enroll in the study and 2) consenting participants who did vs. did not complete the study. Free-text responses from the exit survey will be described qualitatively and used to contextualize our quantitative results and guide future research.

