Aim 3 (exploratory): Assess engagement of the mechanistic target (PTSD symptoms) by the mobile application-based exposure therapy intervention (*Messy Memories*). **Hypothesis:** Participants will report improvement in PTSD symptoms based on pre-/post-intervention decrease in scores on the PTSD Checklist for the Diagnostic and Statistical Manual of Mental Disorders, 5th Edition (PCL-5).

Statistical approach for Aim 3: We will assess whether the *Messy Memories* intervention engages the mechanistic target (PTSD symptoms) by comparing pre-/post-intervention change in PCL-5 score using one-sample t-tests with comparison values of 0 (i.e., all null hypotheses entail no change in PCL-5 score). Given the exploratory nature of Aim 3, we will focus the interpretation of these analyses on effect sizes (Cohen's D) rather than statistical significance to assess potential signals for intervention effects.

Sample size and power estimates: Because the proposed study is a pilot trial, we did not conduct a formal power analysis. We aim to recruit as many participants as possible but selected a minimum n=30 based on pragmatics, the needs of the trial, and previous pilot studies suggesting that this sample size is sufficient to provide an accurate indication of the feasibility and acceptability of the study procedures.

Interim analyses: Given the relatively small sample size of this study and the expected minimal risk of the intervention, no interim analyses are currently planned. However, if concerns arise related to adverse events, then an interim analysis may be conducted and the study may be stopped early depending on the recommendations of the IRB and/or NIA.

Subgroup analyses: Given that this is a stage 1A/1B pilot feasibility study, we do not plan to conduct any pre-specified subgroup analyses.

4. Study Procedures

Provide a detailed description of which procedures are being conducted by Columbia researchers. You may include information about study instruments and study measures.

Recruitment: We aim to enroll ≥ 30 participants in this pilot study. Potential participants will be identified and recruited using several different approaches, each of which is described below.

1. Post-ICU support groups

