- a. Participants will be advised to reach out to the study team if they forget their login.
3. a brief orientation to the app with suggested guidance for usage

Participant App Usage: Participants will be asked to use the Messy Memories app for 6 weeks beginning the day that all components of the Baseline Visit are complete. This date marks the start of the intervention. Participants will be advised of the date which marks the end of the intervention (6 weeks later). They will be asked to focus on their memory of their ICU experience for memory processing. They will be asked to use the app at least 3 days a week for at least 30 minutes each day. They will be instructed to stop using and delete the app from their phones when their study participation ends.

Post-Baseline Check-In: Participants will receive a phone call from study staff within one week of the baseline assessment to confirm that they are not experiencing any technical difficulties with the app. If a participant expresses distress related (or not related) to the app, study staff will follow safety protocol by sharing the IRB-approved list of resources with the participant over the phone and/or via email and will consult with the study PI.

“Visit 2”/3-Week/Mid-Intervention Questionnaire (Approximately 25 minutes): Approximately three weeks after the start of the intervention (Baseline Visit) participants will be asked to complete a questionnaire by telephone or video consisting of the PCL-5, PHQ-8, GAD-7, ASI, IPAQ, and PSQI. If a participant expresses that they will not be available to complete the questionnaire by telephone or video, or if the study team is unable to reach the participant, the study team will send the questionnaire to the participant via Qualtrics. Those who do not complete the survey will remain on the study, and this task will be listed as “not completed” and included as part of analysis.

6-Week/End of Intervention Call: A member of the study team will call the participant within one week prior to the end of the intervention to remind the participant of the date when the intervention ends and that they are to stop using the Messy Memories app at that time. This call can also be used to schedule the 6-week/Post-Intervention Questionnaire.

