“Visit 3”/6-Week/Post-Intervention Questionnaire (Approximately 40 minutes): Approximately six weeks after the start of the intervention (Baseline Visit) participants will be asked to complete another questionnaire by telephone or video consisting of the PCL-5, PHQ-8, GAD-7, ASI, IPAQ, PSQI, substance use measures, implementation measures (e.g., feasibility, acceptability, appropriateness, satisfaction), and qualitative feedback on the intervention (e.g., likes, dislikes, suggestions for improvement). If a participant expresses that they will not be available to complete the questionnaire by telephone or video, or if the study team is unable to reach the participant, the study team will send the questionnaire to the participant via Qualtrics. Those who do not complete the survey will remain on the study, and this task will be listed as “not completed” and included as part of analysis.

“Visit 4”/12-Week/Follow-Up Questionnaire (Approximately 30 minutes): Approximately six weeks after the end of the intervention, participants will be asked to complete one final questionnaire by phone consisting of the PCL-5, PHQ-8, GAD-7, ASI, IPAQ, PSQI, and substance use measures. If a participant expresses that they will not be available to complete the questionnaire by telephone or video, or if the study team is unable to reach the participant, the study team will send the questionnaire to the participant via Qualtrics. Those who do not complete the survey will remain on the study, and this task will be listed as “not completed” and included as part of analysis.

Compensation:

Participants will be compensated a total of \$120 if they complete all components of the study in the form of TruCentive electronic gift cards. This compensation will be allocated in the following amounts:

- \$30 for completion of all components of the Baseline Visit (completing questionnaires, downloading the app, and being onboarded to the app with study staff)
- \$30 for completion of the 3-Week/Mid-Intervention Questionnaire
- \$30 for completion of the 6-Week/Post-Intervention Questionnaire
- \$30 for completion of the 12-Week/Follow-up Questionnaire

Participants who complete only part of a questionnaire (50%, for example) will *not* receive partial compensation for that questionnaire. Participants may, however, skip any question(s) that they do not feel comfortable answering, and this will not impact their compensation for the study.

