If participants incidentally disclose that they are experiencing severe symptoms related to anxiety, depression, psychological distress, or suicidal ideation at any point in the study the study team will follow a standardized safety protocol. This will include reminding participants of available mental health resources provided at the beginning of the study to all participants, offering a phone call with a study PI/MD within 24 hours, encouraging participants to stop using the Messy Memories app if they feel it is causing excessive distress, and encouraging participants to seek medical and/or psychological care with a doctor or mental health professional. All instances of incidentally reported severe psychological distress will be communicated to a Study PI/MD within 24 hours. The Study PI/MD will determine next steps and follow-up with the participant as deemed appropriate.

The study team will collect required demographic data to report to the NIA as required via CROMS (Clinical Research Operations and Management System).

A description of the study will be available on <http://www.ClinicalTrials.gov>, as required by U.S. Law. This website will not include information that can identify participants. At most, the website will include a summary of the results.

References

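### The safety protocol is triggered by distress a participant discloses or expresses; no follow-up PCL-5, PHQ-8 or GAD-7 score has to be reviewed, and no analysis counts participants who worsen

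*Combined protocol and SAP*

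**What the plan says.** Two provisions start the safety protocol. Section 8 (Data and Safety Monitoring) applies throughout the study: "If participants incidentally disclose that they are experiencing severe symptoms related to anxiety, depression, psychological distress, or suicidal ideation at any point in the study". Reports of this kind reach a Study PI/MD within 24 hours. Section 4 (Post-Baseline Check-In) adds a call within one week of baseline, made to check for technical problems, with the condition "If a participant expresses distress related (or not related) to the app".

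The PCL-5, PHQ-8 and GAD-7 are collected at Weeks 3, 6 and 12 (Section 4, Visits 2 to 4). Telephone or video is the default; at Week 12, "participants will be asked to complete one final questionnaire by phone". At all three visits, if the participant is unavailable or cannot be reached, "the study team will send the questionnaire to the participant via Qualtrics". The app also records mood and "their level of distress before and after processing a difficult memory" (Section 2, Data collected).

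Section 2 (Measures) gives cutoffs of 34 on the PCL-5 and 10 on each of the PHQ-8 and GAD-7. They serve to classify: "We will classify participants with PCL-5 scores ≥ 34 as having elevated PTSD symptoms". Under Section 3, "Categorical data will be presented as percentages", and Aim 3 tests "change in PCL-5 score using one-sample t-tests with comparison values of 0", interpreted through Cohen's d.

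**The concern.** The app is self-administered exposure therapy. Section 1 says the authors know of no study of its safety for PTSD caused by critical illness, while citing evidence of safety in other groups, including patients with complex medical conditions. Section 1 also describes avoidance as typical of PTSD, so a protocol that waits for distress to be volunteered is weak in this population.

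The study collects the data that would show deterioration but does not require anyone to act on them. Week 3 is the only scheduled symptom questionnaire before the intervention ends, so it is the only one that could prompt someone to advise stopping the app in time. The pilot is also meant to refine the protocol for a randomized trial, and it would hand that trial no count of participants who got worse.

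**Working it through.** The plan states no figure on this point, so there is none to reproduce. The check is mainly a comparison of provisions, with some arithmetic on size.

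**1. Does any provision require a score to be looked at?**
- Section 8 safety protocol: starts on incidental disclosure of severe symptoms. Severe has no numerical definition. A scheduled questionnaire answer is not plainly incidental, so whether it counts is open.
- Check-in call (Section 4): starts on expressed distress, and comes before Week 3.
- End-of-intervention call (Section 4): a live contact in the last week, for a reminder and scheduling. No score review.
- Weekly staff meetings (Section 8): open to any concern; complaints and confidentiality breaches are singled out. Scores are not named.
- PI withdrawal (Section 7): discretionary.
- Interim analysis (Section 3): possible if adverse-event concerns arise. No score feeds it.
- Cutoffs (Section 2): classification only.

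None requires it.

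**2. A Week 3 questionnaire returned by Qualtrics.** The intervention lasts 6 weeks, so 6 − 3 = 3 weeks remain. At the requested minimum of 3 days a week, that is 3 × 3 = 9 further days of use. The next scheduled live contact is the call between Weeks 5 and 6, two to three weeks later.

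**3. Scores without a review step.** 3 scales × 3 visits × 30 participants = 270 at most. At 70% retention (0.70 × 30 = 21 participants), 3 × 3 × 21 = 189.

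**4. What a mean change can hide.** The documents give no effect size and no SD of change, so these are assumptions. Let change be normal, s its SD, and d the mean improvement divided by s.
- Share whose PCL-5 rises at all = Φ(−d). For d = 0.2, 0.5 and 0.8 this is 42.1%, 30.9% and 21.2%, or 12.6, 9.3 and 6.4 of 30.
- Share rising by at least 10 points = 1 − Φ((10 + d·s)/s). For d = 0.5 and s = 10: 1 − Φ(1.5) = 6.7% (2.0 of 30). For d = 0.5 and s = 15: 1 − Φ(17.5/15) = 12.2% (3.7 of 30). Over d = 0.2 to 0.8 and s = 10 to 15, the range is 3.6% to 19.3% (1.1 to 5.8 of 30).

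Percentages above 34 do not fill this gap. A participant who crosses upward can be offset by one who crosses downward, and a change from 12 to 33 leaves the percentage untouched.

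**5. Precision of a count of worsening (exact binomial 95% CI).** For 0 of n, the upper limit is 1 − 0.025^(1/n): 11.6% for n = 30 and 16.1% for n = 21. For 3 of 30 the interval is 2.1% to 26.5%; for 2 of 21 it is 1.2% to 30.4%.

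**The case against.** The strongest reply is that staff normally hear the answers. Telephone or video is the default, the Section 8 condition runs for the whole study, and a participant who reports severe symptoms to an interviewer may well be treated as having disclosed them. This stands in part: for spoken answers the defect is ambiguity, not absence. A reader might infer that only a volunteered remark can ever start the protocol, or that staff would disregard severe answers they hear. The text supports neither, because it does not say that spoken answers are excluded. The reply does not reach Qualtrics returns.

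A second reply is that the study is minimal risk. Participants may use the app as little as they like, staff speak to them again before the intervention ends, the PI may withdraw them, and an interim look is possible. These narrow the exposure, but none makes anyone read a score.

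A third is that Section 3 disclaims publishing effect analyses and Aim 3 is exploratory. That is a fair reason not to draw conclusions from a count of worsening. It is not a reason to omit one as safety description, and the individual changes will be in the dataset anyway.

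**Conclusion.** The point holds and is worth acting on. Followed exactly, the plan could leave a participant whose scores have risen by Week 3 unreviewed for about three more weeks of exposure. This is clear for Qualtrics returns and uncertain for answers given to staff. The planned analyses would not show how many participants worsened.

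The size is limited to what the text supports: up to 270 scores with no review step at 30 participants with full follow-up, and 189 at 70% retention. The documents give no worsening rate, effect size or SD of change. The shares in step 4 of the working therefore only illustrate that an average improvement can coexist with individual deterioration; they do not forecast it. A reader might infer that the app is harming participants or that many will deteriorate unseen. Nothing in the documents shows either, and without a control arm a rise in score could not be attributed to the app.

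**What to change.** In Section 8:
- State that questionnaire answers, spoken or returned by Qualtrics, count as disclosure.
- Score the PCL-5, PHQ-8 and GAD-7 at the end of the call or on receipt of the form, within one working day.
- Send to the Study PI/MD within 24 hours (a) any score that has risen from its pre-intervention value by at least a margin the sponsor fixes in advance (for example, as an assumption, 10 points on the PCL-5), whether or not it crosses a cutoff, and (b) any score in a severe range fixed in advance, whether or not it has risen. The PI/MD decides whether the Section 8 steps apply.
- Name the pre-intervention values: the screening PCL-5, since the Section 4 baseline visit lists none, and the baseline-visit PHQ-8 and GAD-7.

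Reusing the classification cutoffs as the trigger would be simpler but would not serve. A rule requiring PCL-5 of at least 34 together with any rise would flag 33 to 34, miss 12 to 33, and ignore a severe score that had not risen.

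In Section 3, beside the Aim 3 mean change, report at each visit the number and proportion whose PCL-5 rose by at least the margin, with an exact 95% CI. Label it descriptive and not attributable to the app without a control arm.

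The cost is a short amendment, prompt scoring, one table row per visit and modest PI/MD time. No new measures, visits or participants are needed. Some flags will reflect ordinary fluctuation, and their number cannot be predicted from the documents. The in-app ratings are left out of the rule, because the documents do not say when staff would see them.
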